12.2.2.2 Ablavar Dose and Injection Rate

Each patient in the Ablavar group of our study will receive 0.03 mmol/kg of Ablavar, the FDA approved dose for MR angiography. The Ablavar will be diluted up to 8 fold and injected over 15-20 seconds (86). These dose and injection rates are consistent with our current institutional standard practice.

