13 EVALUATIONS BY VISIT (ONLY 1 VISIT)

13.1 Visit 1 (Day/Week/Month #)

1. Clinical indication for contrast enhanced cardiovascular MRI established by discussion involving the referring clinician and the Investigators or designee.
2. Clinical rationale for Feraheme vs. Ablavar is discussed with the patient's legal guardian(s) by the Investigators or designee in Part I of the study and the patient's legal guardian(s) are given the choice to choose Feraheme vs. Ablavar as the contrast agent. In Part II of the study, the superior contrast agent as determined in Part I of the study will be used and the benefits and risks of undergoing a combination of ventilator-gated MUSIC-MRI and self-gated MUSIC-MRI will be discussed with the patient's legal guardian(s)
3. Obtain written informed consent and HIPAA authorization and assent, if appropriate by the Investigators or designee.
4. Assign the subject a unique screening number.
5. Record demographics data.
6. Record medical history, including a history of hypersensitivity reactions to iron products and iron overload. Screen for inclusion and exclusion criteria.
7. Procedure for sedation and cardio-respiratory support discussed with the anesthesiologist or NICU staff by the Investigator or designee.
8. Patient undergoes general anesthesia with endotracheal intubation or is transported sedated and intubated from the NICU.
9. Record concomitant medications.
10. Perform and record vital signs.
11. Perform and record oximetry.
12. Perform and record results of blood pressure testing.
13. Contrast infusion.
14. Continue monitoring and recording vital signs and oximetry up to 30 min after infusion
15. MRI exam (ventilator-gated MUSIC-MRI for Part I of the study, and both ventilator-gated and self-gated MUSIC-MRI for Part II of the study).
16. Patient recovers from anesthesia/sedation.

It is noted that one or more of Items 1-through-7 may occur on a day different from (prior to) the day of the MRI study. All of these procedures will be included in 'Visit 1' with relevant dates as appropriate.

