14.1.2 AE Relationship to Study Drug

The relationship of an AE to the study drug should be assessed using the following the guidelines in Table 7.

Table 7. AE Relationship to Study Drug

Relationship to Drug	Comment
Definitely	Previously known toxicity of agent; or an event that follows a reasonable temporal sequence from administration of the drug; that follows a known or expected response pattern to the suspected drug; that is confirmed by stopping or reducing the dosage of the drug; and that is not explained by any other reasonable hypothesis.
Probably	An event that follows a reasonable temporal sequence from administration of the drug; that follows a known or expected response pattern to the suspected drug; that is confirmed by stopping or reducing the dosage of the drug; and that is unlikely to be explained by the known characteristics of the subject's clinical state or by other interventions.

Possibly	An event that follows a reasonable temporal sequence from administration of the drug; that follows a known or expected response pattern to that suspected drug; but that could readily have been produced by a number of other factors.
Unrelated	An event that can be determined with certainty to have no relationship to the study drug.

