18.6 Safety Evaluations

AEs, SAEs, AEs resulting in premature withdrawal from the study, AEs of special interest (hypersensitivity reactions and blood pressure changes requiring intervention), and study related adverse events will be listed and summarized by contrast agent group. For the purpose of safety evaluation, the patients in both Part I and Part II who received the same contrast agent will be included in a single safety report. Due to the limited study cohort size and the small anticipated AE rates, no formal inferential statistical analyses will be performed for AEs. However, while the study is too small to expect statistical significance in sub-groups, the efficacy and safety results will be examined by standard age categories (neonates (0-to-1 month of age), infants and toddlers (1 month to 2 years of age) and children (>2 years of age)) and any clinically important differences reported.

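### The causality scale asks for confirmation by stopping or reducing a drug that is given only once, so some post-dose reactions have no valid grade and grading can differ by agent

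*Combined protocol and SAP*

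**What the plan says.** All references are to the combined protocol and SAP. Section 14.1.2, Table 7, has four grades.

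- *Definitely* has two routes. It opens "Previously known toxicity of agent; or an event that follows a reasonable temporal sequence from administration of the drug"; the second route then adds a recognised response pattern, the condition "that is confirmed by stopping or reducing the dosage of the drug", and no other reasonable explanation.
- *Probably* has one route, with all elements joined. Two of them read "that is confirmed by stopping or reducing the dosage of the drug; and that is unlikely to be explained by the known characteristics" of the child's condition, or by other interventions. Nothing limits the stopping condition to cases where it can be applied.
- *Possibly* drops the stopping condition but describes an event with plausible timing and pattern "but that could readily have been produced by a number of other factors".
- *Unrelated* is "An event that can be determined with certainty to have no relationship to the study drug".

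Section 13 provides for one visit with one contrast infusion. Section 12.2.2.1 gives Feraheme over 10 minutes. Section 12.2.2.2 says of the comparator: "The Ablavar will be diluted up to 8 fold and injected over 15-20 seconds"; the dosage text in Section 11.3 allows up to 30 seconds.

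Under Section 12.1, monitoring continues for at least 30 minutes after the infusion, and the medical record is reviewed at 60 days. The grade reaches an analysis in Section 18.6, where "study related adverse events will be listed and summarized by contrast agent group".

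**The concern.** The stopping condition belongs to repeat dosing, where a drug can be withdrawn and the event watched for improvement. With one short administration there is usually nothing left to withdraw. An assessor who applies Table 7 as written cannot use *Probably*, or the second route to *Definitely*, for a reaction that starts after the dose is in.

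At stake are the recorded relationship grades and the study-related summary by agent. Summarising the safety of both agents is the third study objective. If Part I is not significant, Section 7.3 also asks the DMC to weigh safety differences seen in Part I when advising on the agent for Part II. A scale that works differently for the two agents is a poor basis for either use.

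**Working it through.** The plan states no figure on this point, so there is nothing to reproduce. The check sets the grade definitions against the dosing.

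**Step 1. Which grades can a reaction reach?** The first route to *Definitely* is read as free-standing, which is its natural reading.

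| Reaction | *Definitely*, route 1 | *Definitely*, route 2 | *Probably* | *Possibly* | *Unrelated* |
|---|---|---|---|---|---|
| After dosing, known toxicity | yes | no | no | only if other causes are ready at hand | no |
| After dosing, not a known toxicity, other causes ready at hand | no | no | no | yes | no |
| After dosing, not a known toxicity, no other likely cause | no | no | no | no | no |
| During dosing, drug stopped and event improves, not a known toxicity, no other likely cause | no | can be met | can be met | no | no |

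The table assumes that timing and response pattern are satisfied and that a relationship cannot be ruled out with certainty. The third row is the gap: the event fails *Possibly* because nothing else readily explains it, and fails *Unrelated* because that needs certainty. An assessor must leave it ungraded or stretch *Possibly*.

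**Step 2. For how long could dosing still be stopped?** Inputs are the administration times (Sections 11.3, 12.2.2.1 and 12.2.2.2) and the 30-minute minimum of post-dose monitoring (Section 12.1).

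Share = administration time / (administration time + 30 min)

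- Feraheme: 10 / (10 + 30) = 25%
- Ablavar, 15 s: 15 / (15 + 1800) = 0.8%
- Ablavar, 30 s: 30 / (30 + 1800) = 1.6%

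Longer monitoring lowers these shares. They are shares of time, not of reactions; the documents give no distribution of onset times.

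**Step 3. Is stopping informative when it is possible?** Section 15.1 foresees discontinuing treatment for an adverse event, so a Feraheme infusion can be interrupted. Section 4.5 gives an intravascular half-life of 14 hours, so drug already delivered stays in the blood and improvement on stopping is weak confirmation. Even so, the criterion is formally available for one agent and practically not for the other.

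**Step 4. What does the grade change in the output?** Section 18.6 does not say which Table 7 grades make an event study related.

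- If *Possibly* counts, an event placed there instead of *Probably* leaves the related total unchanged; only an ungraded event is lost.
- If *Possibly* does not count, related events can be undercounted.

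**The case against.** The strongest reply is that few events are touched and little depends on them.

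- **Known toxicities have another route.** Section 5.1 names anaphylactoid reactions, hypotension, rash, nausea and vomiting as Feraheme risks, and Table 5 lists reactions for both agents. These can be graded *Definitely* without any stopping test. *Probably* itself needs a recognised or expected pattern, so many candidates for it are already known toxicities. For these the error may even run upward, since the first route sets no timing test. This stands, and it rules out the inference that Table 7 pushes true reactions in general down to *Possibly*.
- **Table 7 is offered as guidelines.** An assessor may use judgement. That is fair, but it is the only causality scale in the documents, and judgement used to fill a gap may differ between assessors.
- **The main safety outputs do not use the grade.** Adverse event incidence is the endpoint in Sections 8.1.3 and 8.2.3. Section 14.2 documents every serious event whatever its cause. Section 18.6 reports special-interest events (hypersensitivity and blood pressure changes needing treatment) separately and plans no inference. This stands.
- **A difference between agents is not shown.** Its size would need onset times, which the documents do not give, and Section 18.6 expects few events. This stands as to size; the unequal availability of the criterion follows from the administration times alone.

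A reader might also infer that no event found at the 60-day review could be graded *Probably*. The documents do not support that: the review date is when an event is found, and an event recorded then may have begun during the infusion.

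**Conclusion.** The point holds as a wording defect in the causality scale. For a reaction starting after the single dose, *Probably* and the second route to *Definitely* are closed. If the reaction is not graded as a previously known toxicity and no other cause is likely, no grade fits.

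The criterion is available for at most 25% of the monitored time with Feraheme and about 1% to 2% with Ablavar, so the same reaction may be graded differently by agent. The number of events affected cannot be estimated from the documents and is probably small.

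The only analysis output exposed is the study-related summary in Section 18.6, and then only if *Possibly* is not counted as related or the event is left ungraded. It would go too far to conclude that the third objective fails or that the agent comparison is biased in a known direction.

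The conclusion rests on reading the first route to *Definitely* as free-standing and the elements of *Probably* as all required. Low priority.

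**What to change.** 1. In Table 7, delete the stopping or reducing clause from *Definitely* and *Probably*, or mark it 'where applicable'. Timing, response pattern and absence of another likely cause then determine the grade, and the event in the third row of the table can be graded.
2. In Section 18.6, state which Table 7 grades count as study related.

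Both are changes of wording to the assessment scale and the analysis text. They alter no treatment, procedure or sample size and are best made before adverse event assessment begins. If grading has already started, events graded under the old wording should be re-graded so that both agents are assessed on one scale.

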14.2 Serious Adverse Experiences (SAE)

An SAE is defined as any AE occurring at any dose that results in any of the following outcomes:

- death
- a life-threatening adverse experience
- inpatient hospitalization or prolongation of existing hospitalization
- a persistent or significant disability/incapacity
- a congenital anomaly/birth defect

Other important medical events may also be considered an SAE when, based on appropriate medical judgment, they jeopardize the subject or require intervention to prevent one of the outcomes listed.

Serious Adverse Experience Reporting

The investigators will document all SAEs that occur (whether or not related to study drug). The collection period for all SAEs will begin after informed consent is obtained and end after procedures for the study visit have been completed. In accordance with the standard operating procedures and policies of the local Institutional Review Board (IRB), the site investigator will report SAEs to the IRB.

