SAFETY EVALUATIONS	
Safety Evaluations:
 
 1. Incidence of acute AE will be monitored. 2. Continuous patient monitoring and recording of vital signs (pre-, during, and at least 30 min-post contrast agent injection) will be provided by expert and specialized staff, including pediatric anesthesiologists and /or staff from the UCLA Neonatal or Pediatric Intensive Care Units. 3. Incidence of other AE up to 60 days post-MRI via a medical record review. 
Procedures to Reduce Risks of Feraheme Infusion:
 
 1. All patients will be screened for contraindications to Feraheme® administration, including a history of allergy to intravenous iron products and iron overload. 2. Performing MRI in newborns to 6 years of age under sedation and/or general anesthesia with airway protection is considered the standard of care at most institutions performing pediatric cardiac MRI for this age group. In the case of a clinically urgent or life-threatening AE during the procedure, there will already be in place full airway protection and support of respiration.

	
3. Patients will undergo continuous monitoring of heart rate, blood pressure, oxygen saturation and ECG tracing for the duration of the MRI procedure and, at a minimum, 30 min after the injection. In the case of a clinically important AE, changes in vital signs will be evident immediately and appropriate treatment initiated. Protocols are in place to deal with acute AEs related to hypersensitivity and/or anaphylaxis.
 
4. The dose of Feraheme® will be up to 4 mg /kg (approximately half the single therapy dose), diluted with saline and infused slowly per FDA guidelines.

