	
3. The patient's legal guardian(s) decide(s) to participate in one of the study groups.4. Patient undergoes general anesthesia per our institutional standard protocol or is transferred from the neonatal ICU already sedated and intubated.5. Patient undergoes cardiovascular MRI (ventilator-gated MUSIC-MRI) using either Feraheme or Ablavar and with continuous monitoring of vital signs and any AEs. AE treatments are delivered as needed.6. Patient recovers from anesthesia or sedation.7. Patient is followed up at 60 days post-MRI via a medical record review to capture any additional AE.
	
Part II:
 
1. Patient is referred for cardiovascular MRI.2. The Investigators discuss with the patient's legal guardian(s) the study design and risks/benefits for either Feraheme or Ablavar administration, depending on the outcome of Part I.3. The patient's guardian(s) provide written informed consent form.4. Patient undergoes general anesthesia per our institutional standard protocol or is transferred from the neonatal ICU already sedated and intubated.5. Patient undergoes cardiovascular MRI (ventilator-gated MUSIC-MRI and self-gated MUSIC-MRI) using the contrast agent determined in Part I and with continuous monitoring of vital signs. AEs are recognized immediately and treatment delivered as appropriate.6. Patient recovers from anesthesia or sedation.7. Patient is followed up at 60 days post-MRI via a medical record review to capture any additional AE.

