12.1 Clinical Assessments

Concomitant Medications

All concomitant medication and concurrent therapies will be documented at the date of study MRI. Dose, route, unit frequency of administration, and indication for administration and dates of medication will be captured.

Demographics

Demographic information (date of birth, gender, race) will be recorded at Screening.

Medical History

Relevant medical history, including history of current disease, other pertinent respiratory history, and information regarding underlying diseases will be recorded at Screening.

Physical Examination

N/A

Vital Signs / Oximetry / Ventilatory Parameters

Continuous heart rate, blood pressure, ECG, pulse oximetry, and end tidal CO_2 will be monitored for the duration of the MRI study and until the subject is recovered or returned to the Intensive Care facility, or for 30 minutes after the infusion, whichever is longer.

Adverse Events

Information regarding occurrence of acute adverse events will be captured throughout the study. Duration (start and stop dates and times), severity/grade, outcome, treatment and relation to study drug will be recorded on the case report form (CRF). Each patient will be followed up via a review of medical record at 60 days after MRI study to capture any additional AEs.

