14.1.1 AE Severity

The National Cancer Institute's Common Terminology Criteria for Adverse Events (CTCAE) Version 4.0 should be used to assess and grade AE severity, including laboratory abnormalities judged to be clinically significant. If the experience is not covered in the criteria, the guidelines shown in Table 6 below should be used to grade severity. It should be pointed out that the term "severe" is a measure of intensity and that a severe AE is not necessarily serious.

Table 6. AE Severity Grading

Severity (Toxicity Grade)	Description
Mild (1)	Transient or mild discomfort; no limitation in activity; no medical intervention or therapy required. The subject may be aware of the sign or symptom but tolerates it reasonably well.
Moderate (2)	Mild to moderate limitation in activity, no or minimal medical intervention/therapy required.
Severe (3)	Marked limitation in activity, medical intervention/therapy required, hospitalizations possible.
Life-threatening (4)	The subject is at risk of death due to the adverse experience as it occurred. This does not refer to an experience that hypothetically might have caused death if it were more severe.

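### Section 14.2 stops SAE collection at the end of the single study visit, although AEs are captured to day 60, so later serious events may miss the SAE summary and the expedited DMC review

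*Combined protocol and SAP*

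**What the plan says.** Section 14.2 sets the SAE window: "The collection period for all SAEs will begin after informed consent is obtained and end after procedures for the study visit have been completed". The same section defines seriousness by outcome, with no time limit: "An SAE is defined as any AE occurring at any dose that results in any of the following outcomes". The sentence just before the window asks the investigators to document every SAE, related or not.

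Section 13 provides for one visit. Its 16 items end with recovery from anesthesia or sedation, and the 60-day review is not among them. Only items 1 to 7 may fall on another day, and that day must precede the MRI. The synopsis gives one day for screening and imaging.

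AE capture runs longer. Section 12.1 says: "Each patient will be followed up via a review of medical record at 60 days after MRI study to capture any additional AEs". The synopsis lists as a safety evaluation: "Incidence of other AE up to 60 days post-MRI via a medical record review". Section 7.1 also gives follow-up of up to 60 days.

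The synopsis puts SAEs on a fast track (report within 48 hours, DMC convened within one week) and AEs on quarterly DMC review. Section 18.6 summarises AEs and SAEs as separate categories by contrast agent, pools Parts I and II for each agent, and gives no time window.

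**The concern.** The two windows do not match. An event between the end of the visit and day 60 can satisfy the SAE definition and be found by the planned record review, yet lie outside the period in which SAEs are collected. Staff who follow the collection-period sentence would record it as an AE only.

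No step in the available text corrects this at day 60. The fields listed for each AE in sections 12.1 and 14.1 are duration, severity, outcome, treatment and relation to study drug. Seriousness is not listed, and section 14.1.1 warns that "a severe AE is not necessarily serious", so the severity grade cannot stand in for it.

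Two things are at stake. The first is the SAE table that serves Objective 3, the safety summary of both agents. Its content would depend on which sentence of section 14.2 the analyst follows. The second is the speed of DMC review. If Part I is not significant, section 7.3 also asks the DMC to weigh observed safety differences when advising on the agent for Part II, so an ambiguous SAE count could feed into that advice.

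**Working it through.** The plan states no figure to reproduce, so the check is mainly a comparison of texts.

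**Windows side by side**

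| Item | Starts | Ends | Source |
|---|---|---|---|
| SAE collection | Informed consent | Completion of visit procedures | 14.2 |
| The visit | Screening steps, possibly before MRI day | Recovery from anesthesia or sedation | 13.1 |
| AE capture | During the study | Record review at day 60 | Synopsis, 12.1 |
| SAE definition | No limit | No limit | 14.2 |
| SAE summary | Not stated | Not stated | 18.6 |

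**Can the 60-day review count as a visit procedure?** The text does not support it. The review is not on the section 13.1 list, and the note there extends Visit 1 backward from the MRI day only.

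**Size of the gap.** Assume the visit ends on the MRI day (day 0), in line with the synopsis.

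- Calendar days from day 0 to day 60: 60 + 1 = 61.
- Days with AE capture but no SAE collection: 61 − 1 = 60.
- Share: 60/61 = 98.4%. Counting 60 days with the first inside the visit gives 59/60, also 98%.

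This is a share of calendar time, not of risk or of events.

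**Children to whom it applies**

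- Part I closed at the interim: 20 + 20 + 40 = 80.
- Full enrolment: 80 + 40 = 120.
- Somewhat more are possible, because section 15.3 replaces subjects who withdraw before images are recorded.

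**Time to DMC review.** The synopsis does not say when either clock starts. Assume both start when the event is recorded.

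- AE track, longest wait for a quarterly review: 365/4 ≈ 91 days.
- SAE track: 7 days.
- Largest difference: 91 − 7 = 84 days, or 12 weeks.

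The documents give no rate of serious events for days 1 to 60, so no number of affected children is derived.

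**The case against.** The strongest reply is that the protocol already covers these events. The SAE definition has no time limit, the investigators are told to document every SAE, and neither the DMC rule in the synopsis nor the summary in section 18.6 is confined to the visit. A death found at day 60 is an AE with a listed outcome, hence an SAE. Outcome is a recorded field, so seriousness will often be evident. On this reading there is an ambiguity, not a demonstrated omission. That is fair as far as it goes, and it is why the point says such events may be left out. But the collection-period sentence refers to all SAEs and directly follows the general duty to document them. The two conflict, and nothing available says which governs.

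A second reply is that section 14.3 (Medical Monitoring) was not available for this review and may contain SAE handling rules; the DMC charter and operations manual were also not seen. That limits what can be said about reporting steps. It does not remove the explicit sentence in section 14.2, which would still need reconciling.

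Third, the safety analysis is descriptive, monitoring is concentrated around the injection, and other routes stay open: quarterly DMC review of AEs, and FDA, IRB and Sponsor reporting (sections 20, 20.2 and 20.5), none of which is tied to the visit. All of this stands. It narrows the point to classification, tabulation and expedited DMC review. The 84 days is also a maximum, for an event recorded just after a quarterly meeting.

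**Conclusion.** The concern holds. Followed literally, section 14.2 leaves a serious event after the visit recorded as an AE but outside SAE collection, so it may be missing from the SAE table in section 18.6 and from the 48-hour and one-week DMC track. The gap covers 60 of 61 calendar days (98%), assuming the visit ends on the MRI day, and applies to all 80 to 120 planned children. The possible delay in DMC review is up to about 84 days, assuming both clocks run from recording. The event would not be lost, no efficacy analysis is affected, and the number of affected children is unknown. The change should be made; it is not critical to the trial's main conclusions.

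**What to change.** Make the windows agree:

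- **Section 14.2:** run SAE collection from informed consent through the 60-day medical-record review.
- **Section 13:** list that review, with an assessment of seriousness for each event found.
- **Section 18.6:** state that SAEs are summarised over this window.
- **Section 14.3:** when amending, confirm that the 48-hour clock runs from the investigator's awareness of the event.

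The cost is a protocol amendment of one sentence and a line in each of two other sections. The record review is already planned, so no visit or procedure is added. The downside is more unrelated SAEs to classify and report, for example after surgery, and possibly more DMC meetings, because the synopsis ties SAEs to convening the DMC within a week. The change aligns classification and tabulation; it does not speed detection of an event first found at day 60.

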PLANNED INTERIM ANALYSES	
Part I
 
After 50% enrollment is achieved in both the test and control groups, the Investigators will convene the DMC and request an interim analysis. The Investigators will not be blinded to the treatment assignment or to the images, but only to the image quality scores, which will be provided by independent experienced readers. If statistical significance is achieved for the primary efficacy endpoint in the interim analyses, the Investigators will close enrollment for Part I and will begin enrollment for Part II. If statistical significance is not achieved during the interim analyses, we will continue recruiting patients into the two groups (Feraheme® and Ablavar®) and the final statistical analyses will require a 0.025 level of confidence to claim statistical significance.
 
Part II
 
There will be no interim analyses in Part II of our study.
 
Safety Evaluations
 
Adverse events (AEs) will reviewed and monitored by the DMC on a quarterly basis. SAEs will be reported within 48 hours and the DMC will be convened within one week to evaluate the protocol.

STATISTICS	
PRIMARY EFFICACY ENDPOINTS:
 
Part I: Diagnostic efficacy study in 80 children (age newborn-6 years old) to compare Feraheme®-enhanced and Ablavar®-enhanced MRI
 
Control Group= Ablavar® + MUSIC-MRI Test Group= Feraheme® + MUSIC-MRI

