7 STUDY DESIGN

7.1 Study Overview

This is an exploratory, investigator-initiated, prospective, open label, case-control, single center, phase IV study that will examine the diagnostic effectiveness of Feraheme® as an MRI contrast agent in pediatric patients with CHD. A total of 120 patients with suspected or known CHD (age newborn to 6 years) of all ethnicities, females and males, will be enrolled. Total duration of subject participation in the imaging study will be approximately 1.5 hours. In general, we expect the pediatric MRI scans to take no more than about 60 minutes once the scan begins. We will also follow up the children for up to 60 days. Total duration of the study is expected to be 5 years. Our study has two parts:

1) Part I is a comparison study between Feraheme®-enhanced MRI and Ablavar®-enhanced MRI. The goal of Part I is to compare the diagnostic efficacy of these two contrast agents for pediatric CHD using our validated technique MUSIC-MRI (1). We hypothesize that Feraheme® provides superior diagnostic effectiveness than Ablavar® for these patients. The duration of Part I is expected to be 3 years.

2) Part II is expected to commence after the statistical significance of the primary endpoint of Part I is confirmed and the goal is to determine the diagnostic efficacy of an MRI pulse sequence (self-gated MUSIC-MRI), which will leverage advanced image reconstruction techniques and

respiratory motion compensation strategies. Self-gated MUSIC-MRI may ultimately enable high-quality free-breathing cardiovascular MRI for pediatric CHD patients who are able to undergo imaging without sedation or general anesthesia (i.e. children >6 years old who can consistently follow verbal instructions during scanning). The duration of Part II is expected to be 2 years.

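### SAE collection closes with the single study visit while AE follow-up runs to day 60, so how a late serious event is counted and escalated depends on the section followed

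*Combined protocol and SAP*

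**What the plan says.** **Serious events.** Section 14.2 defines them by outcome: "An SAE is defined as any AE occurring at any dose that results in any of the following outcomes". The list that follows includes death and new or prolonged hospitalization. The definition has no time limit, and SAEs are to be documented whether or not they are related to the drug. The same section then sets a window: "The collection period for all SAEs will begin after informed consent is obtained and end after procedures for the study visit have been completed".

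**The visit.** Section 13 provides for one visit. Section 13.1 lists 16 items, the last being "Patient recovers from anesthesia/sedation". The 60-day record review is not among them.

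**Adverse events generally.** Four places follow the children to day 60:
- Synopsis, Safety Evaluations: "Incidence of other AE up to 60 days post-MRI via a medical record review"
- Synopsis, Abbreviated Study Flow, both parts: "Patient is followed up at 60 days post-MRI via a medical record review to capture any additional AE"
- Section 7.1: "We will also follow up the children for up to 60 days"
- Section 12.1: "Each patient will be followed up via a review of medical record at 60 days after MRI study to capture any additional AEs"

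**Use of the SAE label.** Under Planned Interim Analyses, the synopsis says: "SAEs will be reported within 48 hours and the DMC will be convened within one week to evaluate the protocol". AEs in general go to the DMC quarterly. Section 18.6 lists and summarizes AEs and SAEs by contrast agent, pooling Parts I and II, and names no time window for either.

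**The concern.** The plan looks for adverse events for 60 days but stops collecting serious ones when the child recovers from anesthesia. A readmission on day 20 would be found by the planned record review and would be an SAE by definition, yet it falls after the SAE collection period in the same section has closed. No supplied section says how such an event is handled.

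Two things are at stake. The first is the SAE summary by agent. Summarizing the safety of both agents is one of the three study objectives, and if Part I is not significant, section 7.3 asks the DMC to weigh safety differences seen in Part I when advising on the agent for Part II. Two analysts, one following 14.2 and the other 12.1, could report different SAE counts from the same records. The second is escalation. The synopsis ties the 48-hour report and the one-week DMC meeting to SAEs, so it is unclear whether a late serious event starts either.

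**Working it through.** This is a comparison of text; the plan states no figure on this point to reproduce.

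1. **When does SAE collection end?** Section 14.2 ends it with the procedures of the study visit. There is one visit, and its last listed item is recovery from anesthesia or sedation. The closing note in 13.1 lets items 1 to 7 fall before the MRI day, which extends the visit backward only. The synopsis allots 1 day to screening and imaging.

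2. **When does AE capture end?** At 60 days after MRI, in all four places quoted above. If the visit ends on the imaging day (an assumption, in line with step 1), AE capture outlasts SAE collection by about 60 days per child. At full enrolment that is at most 120 × 60 = 7,200 child-days. If Part I stops at the interim, with 20 + 20 children plus 40 in Part II, it is 80 × 60 = 4,800.

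3. **Apply both to a readmission on day 20.**

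| Question | Following the 14.2 window | Following the 14.2 definition with 12.1 |
|---|---|---|
| Recorded as an AE? | Yes, under 12.1 | Yes |
| Within SAE collection? | No | Yes |
| In the SAE summary of 18.6? | No | Yes |
| 48-hour report and one-week DMC meeting? | Not triggered | Triggered |
| In the quarterly DMC review of AEs? | Yes | Yes |

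Section 18.6 cannot settle the third question because it names no window.

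4. **Effect of one such child on the SAE summary.** This needs no assumed event rate. Because 18.6 pools by agent, the planned denominators at full enrolment are 40 + 40 = 80 for the agent carried into Part II and 40 for the other. One child in or out moves the SAE proportion by 1/80 = 1.25 or 1/40 = 2.5 percentage points. After an interim stop the denominators are 20 + 40 = 60 and 20, and the shifts are 1/60 = 1.7 and 1/20 = 5.0 points.

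5. **How many children?** Unknown. The documents give no rate of serious events over 60 days. Only events after the visit count here, since earlier ones are SAEs on either reading.

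**The case against.** The best case against is that this is a drafting inconsistency with little practical effect, and most of that stands. Late events are still found and recorded (12.1) and reviewed quarterly by the DMC. FDA expedited reporting (section 20), IRB reporting of serious events regardless of causality (20.2) and the duty to report AEs to the sponsor (20.5) carry no visit-end limit. Section 14.2 also obliges investigators to document every SAE that occurs, and an analyst could reasonably apply the definition to all AEs captured through day 60. Safety is descriptive, so type I error and power are untouched.

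A reader might therefore infer too much: that late deaths and readmissions go unrecorded, or that the protocol exempts them from reporting. The documents do not support that, given the routes just listed. Nor do they support a claim that many children would be affected, since no rate is given.

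What the objection does not remove is the conflict itself. None of those routes decides which events belong in the SAE summary or whether the one-week DMC meeting is called. The FDA route covers suspected reactions, so an event judged unrelated does not reach the agency that way. The quarterly review could leave about three months before the DMC sees an event for which the SAE rule requires a meeting within one week.

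Section 14.3 (Medical Monitoring) appears in the contents list but was not in the supplied text. It may bear on escalation, and nothing can be inferred from its absence.

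**Conclusion.** The point holds as an internal conflict. Taken literally, 14.2 keeps a serious event found at the 60-day review out of SAE collection although it meets the SAE definition, and the supplied text does not resolve this. The consequence is confined to the SAE count by agent and the 48-hour and one-week steps; capture of the event as an AE is not affected. The number of children is unknown, but with planned denominators of 20 to 80 per agent a single reclassified child shifts the reported SAE proportion by about 1 to 5 percentage points.

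The conclusion assumes that the visit ends where the 13.1 list ends. Confidence is high for the conflict in the text and lower for escalation, because 14.3 could not be read. The plan should be corrected, but no efficacy conclusion depends on it.

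**What to change.** - **14.2:** end the SAE collection period at the 60-day post-MRI record review, and state that serious events found there are reported within 48 hours of the investigator becoming aware of them. Leave the DMC rule in the synopsis unchanged.
- **13.1:** add the day-60 record review for AEs and SAEs to the listed procedures.
- **18.6:** state that AEs and SAEs are summarized by agent through day 60.

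This takes a few lines of text and no added visit, since the record review is already planned for every child. The downside is that more events will be classified and reported as SAEs and may convene the DMC. Surgical complications will be among them, because these children are imaged to inform surgical decisions. In return the trial has a single SAE count and a single escalation rule.
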